5.5. PHARMACOKINETIC ASSESSMENTS

PK assessments will include analysis of GLPG1690. Plasma concentrations of GLPG1690 will be measured using a validated LC-MS/MS method, and will be performed by the bioanalytical laboratory in charge of these analyses (██████████).

Other measurements (e.g., metabolism studies, stability studies) may be performed if deemed appropriate.

5.5.1. Biological Samples

Blood samples of 1 mL will be collected by venipuncture (or indwelling catheter for pharmacokinetic sampling day) in the arm at the time points indicated in the study flow chart (provided in Section 1) and according to sequence of study assessments as described in Section 5.1.

All details on sample handling and shipment instructions will be provided in a separate laboratory manual.

5.5.2. Pharmacokinetic Parameters

PK parameters will be derived with Phoenix WinNonlin (Version 6.2 or higher).

The following PK parameters, where appropriate, will be determined using non-compartmental analysis for GLPG1690 from individual concentration-time profiles in plasma:

- C_{\max} maximum observed plasma concentration
- t_{\max} the time of occurrence of C_{\max}
- $AUC_{0-\tau}$ area under the plasma drug concentration-time curve of a dosing interval

– C_{τ} trough plasma concentration (just before the next dosing i.e. predose sample)

Additional PK parameters may be calculated if appropriate.

5.6. PHARMACODYNAMIC ASSESSMENTS

5.6.1. Biological Samples (Blood)

Blood samples of 2 mL will be collected by venipuncture (or indwelling catheter for pharmacokinetic sampling days) in the arm at the time points indicated in the study flow chart (provided in Section 1) and according to sequence of study assessments as described in Section 5.1.

All details on sample handling and shipment instructions will be provided in a separate laboratory manual.

5.6.2. Biological Samples (BALF)

Bronchoscopies for the collection of BALF samples will be conducted (post dose if applicable) at the time points indicated in the study flow chart (provided in Section 1) and according to sequence of study assessments as described in Section 5.1.

All details on sample collection through bronchoscopy will be provided in a separate, study-specific bronchoscopy/BALF manual. All details on sample handling and shipment instructions will be provided in a separate laboratory manual.

5.6.3. Pharmacodynamic Parameters

LPA species (C18:2) will be determined in plasma. Other LPA species might be analyzed if deemed appropriate.

All detectable LPA species will be determined in the supernatant of the BALF.

5.7. EXPLORATORY EFFICACY ASSESSMENTS

5.7.1. Pulmonary Function by Spirometry

Pulmonary function will be assessed through spirometry both performed at the study center (at screening, baseline, and thereafter post dose at the time points indicated in the study flow chart [provided in Section 1] and according to sequence of study assessments as described in Section 5.1) and at home (at baseline and thereafter post dose; on a daily basis in the morning). Specific instructions on how to perform the spirometry at home are provided in a separate spirometry user manual.

The site-based spirometry must meet the criteria for acceptability and repeatability as defined in the ATS/ERS guidelines (Miller, Hankinson, & Brusasco, 2005)

Pulmonary function will be measured in standardized manner, results will be transmitted electronically and confirmed by a central reader.

Timing of home- and site-based spirometry

The spirometry test is to be performed in the morning, preferably at approximately the same time (± 1 h) every day/visit.

Timing of home- and site-based spirometry versus bronchodilator use

All spirometry evaluations should be performed pre-bronchodilator. Pre-bronchodilator spirometry is defined as spirometry testing performed for a subject who has:

- withheld their short-acting β -agonist (e.g., albuterol) or anticholinergic (e.g., ipratropium bromide) for >6 h prior to the spirometry assessment AND
- withheld their long-acting bronchodilator (e.g., salmeterol, formoterol) for ≥ 12 h and other longer-acting agents (e.g., indacaterol, tiotropium) for ≥ 24 h prior to the spirometry assessment

In case the subject is on bronchodilators, he/she can use the bronchodilator after the spirometry but prior to HRCT for FRI parameters.

Spirometry parameters and calculation of predicted values

The following parameters will be measured as part of the spirometry assessment:

- FEV₁ (L) and percent predicted FEV₁
- FVC (L) and percent predicted FVC
- FEV₁/FVC ratio
- Forced expiratory flow (FEF) between 25 and 75% of exhaled volume (FEF₂₅₋₇₅)

The '2012 Global Lung Function Initiative Equations' will be used to estimate the predicted values (Quanjer, et al., 2012).

5.7.2. Biomarker Analysis

5.7.2.1. Biological Samples (Blood)

Blood samples of 14 mL will be collected predose by venipuncture (or indwelling catheter for pharmacokinetic sampling days) in the arm at the time points indicated in the study flow chart (provided in Section 1) and according to sequence of study assessments as described in Section 5.1.

All details on sample handling and shipment instructions will be provided in a separate laboratory manual.

5.7.2.2. Biological Samples (BALF)

See Section 5.6.2 for details on bronchoscopies.

5.7.2.3. Biomarkers to be Analyzed

The following exploratory biomarkers will be evaluated in blood samples:

- KL-6/Muc1
- surfactant protein A and D
- CCL18
- ATX
- MMP1, MMP7
- markers of extracellular matrix (ECM) turnover (neoepitope assay)

The following additional biomarkers may be analyzed in blood samples if deemed appropriate after results of the above exploratory markers have become available:

- oxydative stress: ICAM-1 and VCAM-1
- neutrophil recruitment, activation: IL8, S100A12
- other biomarkers might be analyzed if deemed appropriate (e.g., serique protein, serique miRNA)

ATX will be determined in the supernatant of the BALF. Bronchoalveolar lavage (BAL) cell count will be performed. BAL cell pellets will be stored for possible future analyses (transcriptomics, proteomics).

5.7.3. Quality of Life

The SGRQ will be completed predose at the time points indicated in the study flow chart (provided in Section 1) and according to sequence of study assessments as described in Section 5.1.

The SGRQ is a 50-item questionnaire split into 3 domains: symptoms (assessing the frequency and severity of respiratory symptoms), activity (assessing the effects of breathlessness on mobility and physical activity), and impact (assessing the psychosocial impact of the disease). Scores are weighted such that every domain score and the total score range from 0 to 100, with higher scores indicating a poorer health-related quality of life.

Subjects must be able to read and complete the SGRQ by themselves. They should not receive any help from anyone (such as family and friends) or study staff in interpreting or responding to the questions. The study staff will review the questionnaires after completion to ensure that all questions are completed. In case of missing information, the subject will be asked to complete the missing items.

5.7.4. Functional Respiratory Imaging

HRCT will be performed (post dose if applicable) at the time points indicated in the study flow chart (provided in Section 1) and according to sequence of study assessments as described in Section 5.1. HRCT scans will be used to generate FRI measurements allowing for an evaluation of regional IPF disease manifestation and disease progression. In case the subject is on bronchodilators, he/she can use the bronchodilator after the spirometry but prior to HRCT for FRI parameters.

At each computed tomography (CT) assessment an inspiratory and an expiratory scan will be taken. During the baseline visit an additional scan of the upper airway will be taken. The inspiratory and an expiratory scan will expose the subject to a total radiation dose of approximately 4-5 mSv per visit, including the initial CT localizer radiograph (topogram scout). The upper airway scan will expose a subject to approximately 1 mSv. A radiation dose of approximately 2-2.5 mSv is equivalent to approximately 1 year of background radiation (based on the assumption of an average "effective dose" from natural background radiation is of 3.1 mSv per year in the US and 2.4 mSv per year in Europe. (USNRC, 2014; WNA, 2015)

All CT images will be imported into [REDACTED]

[REDACTED] for analysis. This software package converts the HRCT images into patient specific, 3-dimensional computer models of the lung lobes, the airway lumen and wall, and the vascular tree. The airway and vascular tree are evaluated at functional residual capacity (FRC) and total lung capacity (TLC) level and can be segmented down to bronchi/vessels with a diameter of around 1-2 mm. Beyond this point the HRCT resolution is insufficient to distinguish alveolar and intraluminal air, or blood vessel tissue and surrounding lung tissues. A typical airway model includes 5-10 generations, depending mainly on the disease state of the individual patient. Afterwards the airway lumen models will be processed further to obtain a model that is suitable for flow calculations.

The following FRI parameters based on low-dose inspiratory-expiratory multi-slice CT images and computational fluid dynamics flow simulations will be evaluated.

- lobar volumes at FRC and TLC
- airway volumes at FRC and TLC
- airway resistance
- internal lobar airflow distribution
- low attenuation or emphysema score at TLC
- blood vessel density or fibrosis score at TLC
- airway wall thickness at TLC
- air trapping at FRC
- mass of deposited particles per defined airway section

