EVENT	Visit 1 Screening	Visit 2 Baseline	DOSING PERIOD						EDV	FU
				Visit 3 ¹ W1	Visit 4 ¹ W2	Visit 5 ¹ W4	Visit 6 ¹ W8	Visit 7 ¹ W12		
Visit										
Study days (D)	D-28 to D-4	D-1	D1	D7 ±2 days	D14 ±2 days	D28 ±3 days	D56 ±3 days	D84 ±3 days		D98 ±3 days
PD blood samples ¹¹ (LPA)		X				X		X	X	X
Biomarker blood samples ¹²		X				X		X	X	X
BALF sample (bronchoscopy)		X						X	X ¹³	
Spirometry ¹⁴	X	X		X	X	X	X	X	X	X
Home-based spirometry		X	On a daily basis							
SGRQ		X				X		X	X	X
HRCT ¹⁵		X						X	X	
(S)AE assessment			Throughout the study							
Concomitant medications			Throughout the study							

AE=adverse event; BALF=bronchoalveolar lavage fluid; D=day; DLCO= diffusing capacity for the lungs for carbon monoxide; ECG=electrocardiogram; EDV=early discontinuation visit; EOS=end of study; FU=follow-up; FRI=functional respiratory imaging; FSH=follicle stimulating hormone; HRCT=high-resolution computed tomography; LPA=lysophosphatidic acid; PD=pharmacodynamics; PK=pharmacokinetic; SAE=serious adverse event; SGRQ=St George's Respiratory Questionnaire; SLB=surgical lung biopsy; W=week

¹¹ All PD samples will be taken predose. At Day 28, in addition to predose, samples will be taken 1.5 h and 6 h post dose

¹² All blood samples will be collected predose.

¹³ If feasible for the subject

¹⁴ All spirometry evaluations should be performed prior to administration of bronchodilator.

¹⁵ To measure FRI parameters. During the baseline visit an additional scan of the upper airway will be taken.

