5.3. SUBJECT DIARY CARD

Subjects will be given a diary card at Day -1 (baseline) to record the following:

- From Day 1 through Day 84 (or the EDV), subjects will be asked to record the date (and time) of study drug intake and the number of capsules taken for each administration.
- From Day 1 to Day 84 (or the EDV), subjects will be asked to indicate whether a home-based spirometry test was done and if no such test was done, the reason(s) why should be provided.

¹⁶ Subjects taking inhaled bronchodilators can do this after spirometry assessments (and DLCO) and prior to the performance of the HRCT.

- From Day 1 to Day 84 (or the EDV), subjects will be asked to record changes in concomitant medication regimen, including new medicines not captured in medication history, use of bronchodilators, any other concomitant medication used as well as any emerging AE.

Subjects will be instructed to bring the diary card and used/unused study drug to each visit. All diary card data will be entered in the eCRF by the designated site personnel.

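### For subjects on bronchodilators, use before each HRCT is optional, so the baseline and follow-up scans behind the FRI change can be taken in different bronchodilator states

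*Protocol*

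**What the plan says.** The rule on bronchodilators before imaging appears three times in the protocol, each time as a permission.

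- Section 5.7.4 (Functional Respiratory Imaging): the subject on bronchodilators is told that "he/she can use the bronchodilator after the spirometry but prior to HRCT for FRI parameters".
- Section 5.7.1 (Pulmonary Function by Spirometry): "In case the subject is on bronchodilators, he/she can use the bronchodilator after the spirometry but prior to HRCT for FRI parameters".
- Footnote 16 to the Section 5.1 sequence of assessments, printed with Section 5.3: "Subjects taking inhaled bronchodilators can do this after spirometry assessments (and DLCO) and prior to the performance of the HRCT".

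Spirometry is treated differently. Section 5.7.1 states that "All spirometry evaluations should be performed pre-bronchodilator" and gives a withholding time for each class of agent: more than 6 h, at least 12 h or at least 24 h.

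The flow chart places the HRCT at baseline (Day -1), Week 12 and the early discontinuation visit, and its footnote gives the purpose: "To measure FRI parameters. During the baseline visit an additional scan of the upper airway will be taken". The FRI parameters in Section 5.7.4 include "airway volumes at FRC and TLC", "airway resistance" and "air trapping at FRC". Change in FRI parameters is a secondary objective (Section 3.2).

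**The concern.** Section 2.6 adds FRI because 12 weeks may be too short for FVC to show a difference. For each subject the FRI change rests on one baseline scan and one later scan, so there are no repeat scans to average out a difference in measurement conditions.

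A bronchodilator acts on airway calibre, and several listed parameters measure calibre or follow from it. If a user is scanned withheld at one visit and bronchodilated at the other, the bronchodilator response enters that subject's change from baseline. Nothing in the planned model separates it from disease change: the covariates in Section 6.3.6 are baseline FVC, baseline DLCO, age, gender, treatment group, country and baseline value.

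This is a rule for acquiring the scans, so it belongs in the protocol. An analysis plan can flag an unmatched pair or set it aside, but it cannot produce a matched pair that was never scanned.

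**Working it through.** The protocol states no figure on this point and no power calculation (Section 6.1), so there is nothing to reproduce. The check has a textual part and an illustrative part.

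**Textual check**

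1. *State on arrival at the scan.* Section 5.1 orders spirometry, DLCO, then HRCT. Spirometry requires withholding, so a compliant user finishes spirometry in the withheld state at every visit.
2. *What happens next.* The three statements let the user take the drug or not before the HRCT. If taken, the scan is bronchodilated; if not, it is withheld. Both comply.
3. *Link between visits.* None of the three statements fixes the agent or the interval to the scan, or requires the later scan to match the baseline scan. Withheld at Day -1 and bronchodilated at Day 84, or the reverse, is within protocol.
4. *Stable medication.* Section 4.3.7 requires long-term medication to be stable before entry and kept at the same dose and schedule. It does not govern whether an intake falls between spirometry and the scan.
5. *Recording.* The diary in Section 5.3 covers bronchodilator use from Day 1, after the baseline scan. Section 4.3.7, however, requires the name, dose, route, dates and times of other treatments in the eCRF, with recording from consent. Day -1 is therefore covered. Recording shows the state but does not control it.

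**Size for one discordant subject**

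Inputs: about 24 subjects randomized 3:1 (Section 4.3.3).

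- Active arm: 24 × 3/4 = 18. Placebo arm: 24 × 1/4 = 6.
- Let b be the subject's bronchodilator response in an FRI parameter. One discordant subject moves the arm mean by b/n: b/6 on placebo, b/18 on active.
- Standard error of the unadjusted difference in mean change: SD × √(1/18 + 1/6) = 0.471 SD.

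The documents give no value for b. Assumed range: 0.5 to 2 SD of the change.

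| Discordant subject | b = 0.5 SD | b = 1 SD | b = 2 SD |
|---|---|---|---|
| One on placebo: shift (SD) | 0.083 | 0.167 | 0.333 |
| One on placebo: shift / 0.471 (SE) | 0.18 | 0.35 | 0.71 |
| One on active: shift (SD) | 0.028 | 0.056 | 0.111 |
| One on active: shift / 0.471 (SE) | 0.06 | 0.12 | 0.24 |

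Two placebo subjects discordant in the same direction double the placebo row, to 0.35, 0.71 and 1.41 SE. Two in opposite directions with equal responses cancel in the mean but still add variance. With no bronchodilator users, every entry is zero.

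The standard error is unadjusted. The planned mixed-effects ANCOVA would give a somewhat different value, but the 6-versus-18 contrast remains.

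**The case against.** The case for leaving the text alone has five parts.

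- **Few subjects may be affected.** The permission covers only subjects already on bronchodilators. Inclusion criterion 6 requires a pre-bronchodilator FEV1/FVC of at least 0.70, which excludes obstruction on that ratio. The number of users is not given and could be nil. This stands and limits the point.
- **Much is already standardized.** Visits are in the morning at about the same time, the order of assessments is fixed, the same withholding applies before each spirometry, and long-term regimens must be stable. This also stands. It narrows the gap to one possible intake between spirometry and scan, but does not close it.
- **Intake times are already recorded.** True under Section 4.3.7, so no new data field is needed. A record allows flagging, but it does not match the scans.
- **FRI comparisons are exploratory and the trial is not powered.** True, and a reason to keep the point modest. It is not a reason to accept avoidable noise when the correction costs almost nothing.
- **Matching may be impossible at some early discontinuation visits.** After an acute exacerbation Section 4.3.7 leaves all treatment options open. This stands, and the requirement has to allow for it.

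Three stronger readings are tempting, and the documents support none of them. A reader might infer that discordance biases the treatment comparison in one direction. The trial is randomized and double-blind, and nothing in the text links the choice to arm or gives it a direction. A reader might take the diary as leave to start a bronchodilator during the study. Section 5.3 only asks for such use to be recorded; new medication is governed by Section 4.3.7, which calls for a risk/benefit assessment. A reader might extend the problem to every FRI parameter. The argument reaches those that depend on airway calibre and makes no claim about others, such as the fibrosis score.

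**Conclusion.** The point holds for bronchodilator users. The protocol fixes the bronchodilator state for spirometry and leaves it open for the HRCT minutes or hours later, with no link between a subject's scans. The consequence is avoidable within-subject noise in the calibre-dependent FRI parameters and possible chance imbalance, mainly in the placebo arm of about 6.

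The size is modest and conditional. On the assumed responses, one discordant placebo subject moves the comparison by less than one standard error, and one active subject by about a third of that. The conclusion rests on three assumptions: at least one randomized subject uses a bronchodilator, that subject's choice differs between scans, and the drug measurably changes the parameter. The documents give no frequency or size for any of these. It is a worthwhile clarification to a secondary-objective measurement and does not threaten the trial's primary objectives.

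**What to change.** In Section 5.7.4, Section 5.7.1 and footnote 16, replace the permission with one common requirement: where feasible, each subject's Week 12 or early discontinuation HRCT is done in the same bronchodilator state as the baseline HRCT, with the same agent and a similar interval to the scan. The sponsor decides which state.

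Use the intake times already required by Section 4.3.7, including those on Day -1, to identify discordant pairs, and repeat the FRI analysis without them as a sensitivity analysis.

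The cost is the same short edit in three places and a check of intake times at each scan. No extra scan, visit or data field is needed. Some pairs, for example at early discontinuation after an exacerbation, may not be matchable and would only be flagged.

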5.8. TOTAL BLOOD VOLUME

The estimated total volume of blood that will be collected for each subject throughout the study is maximum 215 mL.

If deemed necessary by the investigator (see Section 5.4.2), additional samples may be obtained to ensure the safety of the subject. Due to this possibility, the blood volumes described above are a best estimation.

After the study is completed, any left-over blood samples may be stored under the control of the sponsor. These samples may be used by the sponsor/partner, or by other companies

belonging to the sponsor for future research on the mode of action of GLPG1690 and/or future research in IPF.

6. STATISTICAL METHODS

All statistical calculations will be performed by the CRO using the SAS (Version 9.1.3 or higher) software for statistical computations and SAS for graphical purposes.

The statistical analysis and visualization of the FRI parameters will be implemented in R version 3.0.2 or higher (The R Foundation for Statistical Computing, Vienna, Austria) by [REDACTED]

All statistical methods will be detailed in a statistical analysis plan that will be finalized prior to the database lock.

All data collected in this study will be documented using summary tables, figures and subject data listings.

6.1. DETERMINATION OF SAMPLE SIZE

Strict statistical criteria were not used to determine the sample size for this study. The number of subjects included in this study should give reasonable precision around the estimates derived for the safety, PK, and PD evaluation.

6.2. POPULATION FOR ANALYSES

6.2.1. All Screened Subjects

All subjects who signed an ICF.

6.2.2. All Randomized Subjects

All subjects randomized into the study.

6.2.3. Safety Analysis Set

All randomized subjects who received at least 1 dose of study drug.

6.2.4. Pharmacokinetics Analysis Set

All randomized subjects who received at least 1 dose of study drug and for whom evaluable PK data were available. Subjects with a protocol deviation that may impact the PK results will be excluded from this population.

6.2.5. Pharmacodynamics Analysis Set

All randomized subjects who have at least one dose of study drug and have at least one post-baseline assessment with PD data.

6.2.6. Intent to Treat Analysis Set

All randomized subjects who have at least one dose of study drug and have at least one post-baseline assessment with exploratory endpoint data.

6.3. STATISTICAL ANALYSES

6.3.1. General Statistical Considerations

Summary tabulations will be presented and will display the number of observations, mean, standard error (SE), median, minimum, and maximum for continuous variables, and the number and percentage per category for categorical data. In addition to tabulated descriptive statistics, graphical data displays may be used to summarize the data. Unless otherwise noted, inferential statistics will be interpreted at the 2-sided 5% level. Data will be pooled across centers and countries.

No formal interim analysis is planned for this study.

